5.2. General Methods

Continuous data will be described using descriptive statistics such as the number of observations (n), mean, standard deviation, standard error, median, quartiles, minimum, and maximum. For the summary statistics of all numerical variables unless otherwise specified, minimum and maximum will be displayed to the same level of precision as reported. Median and mean will be presented to the level of precision collected in the database plus one additional decimal. The standard deviation and standard error will be presented to the level of precision collected in the database plus 2 additional decimals. For any assessments with repeated collections at a given study visit (e.g. height) the mean will represent the value at that visit unless otherwise noted. For biomarker and/or lab data, if any value is recorded as <lower limit of quantitation (LLOQ) then the value used for calculations will be assigned a value of LLOQ.

Categorical and ordinal data will be described using the patient count and percentages in each category. When count data are presented, the percentage will not be presented when the count is zero.

Summary tables and figures for each study period will include all data collected during the corresponding period as defined in Section 4.1.

The per-patient listings will include all data collected during each study period. For per-patient listings of the duration of study, there will be a variable to indicate the period of the data collection (Primary Analysis Period or Extension Period).

Day 1 will be defined as the day of the first dose of lumasiran. Study day is calculated relative to the first dose date of lumasiran for all patients:

If the assessment date is after the date of first lumasiran dose, then the study day will be calculated as:

$$\text{Study Day} = \text{Date of assessment} - \text{date of first dose of lumasiran} + 1,$$

If the assessment date is before the date of the first dose of lumasiran, then the study day will be calculated as:

$$\text{Study Day} = \text{Date of assessment} - \text{date of first dose of lumasiran}$$

At a minimum, all listings will include the following variables:

- Baseline: relative to first dose of lumasiran (Section 5.4).
- Study Day: relative to first dose of lumasiran.
- Visit labels: visits based upon actual study visits (Section 5.6).

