7.3. Secondary Endpoints

For efficacy secondary endpoints, the Efficacy Analysis Set will be used; for PK secondary endpoints, the PK Analysis Set will be used.

Secondary endpoints in this study are as follows:

Extension Period (Month 6 to End of Study)

Percent change in spot urinary UOx:Cr ratio from baseline for all post-Month 6 visits will be summarized descriptively using the Efficacy Analysis Set. The analyses for 24-hour urinary oxalate corrected for BSA and 24-hour urinary UOx:Cr ratio will be carried out using Extension Period data as well.

Duration of Study (Baseline to End of Study)

Absolute changes in spot urinary UOx:Cr ratio and percent and absolute change in plasma oxalate from baseline using Efficacy Analysis Set will be performed similarly to primary analysis. In addition, percent and absolute change in plasma oxalate from baseline will also be analyzed using only patients in the Efficacy Analysis Set whose baseline plasma oxalate $\geq 1.5^*LLOQ$. LS means by postdose visits with corresponding SEM and 95% CIs will be displayed for the primary analysis period.

For continuous endpoints (including eGFR), descriptive statistics will be generated at each scheduled visit. Mean (+/- SEM) figures of actual values and changes from baseline will be plotted as well as individual spaghetti plots and listings. For binary endpoints, the number and associated percent of patients who met each threshold (e.g. $\leq ULN$ or $\leq 1.5 \times ULN$) at visits will be presented.

To demonstrate durability of the effect of lumasiran, for binary endpoints, (e.g. proportion of patients with spot urinary UOx:Cr ratio level $\leq ULN$ or $\leq 1.5 \times ULN$), tabular summaries of the number and percent of patients who met the threshold at post-baseline visits will be presented.

An analysis of the percentage of time that spot urinary UOx:Cr ratio is at or below the near-normalization threshold for the duration of study will be summarized. A patient is considered to have met the threshold if the spot urinary UOx:Cr ratio is $\leq 1.5 \times ULN$ at a post-baseline visit.

For each patient, the percentage of time that spot urinary UOx:Cr ratio is at or below the near-normalization threshold of $\leq 1.5 \times ULN$ will be calculated as follows:

$$\frac{\text{cumulative time at or below near normalization threshold}}{\text{cumulative time of valid assessments}} \times 100$$

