where cumulative months in near-normalization will be defined as the summation across all intervals that met the near-normal threshold and cumulative months of valid assessments will be defined as the summation across all valid post-baseline collections.

Given that the sample collection varies during the study, the calculation of percentage of time will include the following considerations:

- Time will include all follow-up assessments until study end or premature treatment discontinuation, whichever occurs first.
- A linear interpolation method will be used to determine the bookend dates at which the patient crossed into the normal threshold and crossed out of the normal threshold

Descriptive statistics of percentage of time at or below the threshold (among the subset of patients who had at least one post-baseline value that met threshold) will be presented. In addition, the number of patients and associated percentage of patients in each category (e.g. <25%, ≥25% to <50%, ≥50% to <75%, ≥75% of time at or below the threshold) will also be presented.

Descriptive statistics of eGFR at and after 6 months of lumasiran will be presented using the Efficacy Analysis Set and Safety Analysis Set. Shift tables of eGFR categories from baseline to post-baseline visits and an overall worst post-baseline will also be generated

To demonstrate durability of the treatment effect of lumasiran, additional secondary endpoints may be assessed.

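### SAP 7.3 limits the mean, SD, median and quartiles of percentage of time at or below 1.5×ULN to patients who met the threshold at least once, and plans this Extension Phase endpoint only over the whole study.

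*SAP*

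**What the plan says.** Protocol Section 2 and SAP 3.2 both list percentage of time at or below 1.5×ULN under Extension Phase, which the protocol labels as Month 6 to End of Study. Neither attaches a success condition to it. SAP 4.1 starts the extension period after the Month 6 dose.

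SAP 7.3 then makes these statements:

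- Population: "For efficacy secondary endpoints, the Efficacy Analysis Set will be used".
- Extension Period block: "Percent change in spot urinary UOx:Cr ratio from baseline for all post-Month 6 visits will be summarized descriptively using the Efficacy Analysis Set". The 24-hour measures are added there. Percentage of time is not mentioned.
- Duration of Study block: the percentage of time that the ratio "is at or below the near-normalization threshold for the duration of study will be summarized".
- Time base: "cumulative months of valid assessments will be defined as the summation across all valid post-baseline collections". No Month 6 start is given. "A linear interpolation method will be used to determine the bookend dates" at which a patient crosses the threshold.
- Descriptive statistics are given "among the subset of patients who had at least one post-baseline value that met threshold".
- A second table gives "the number of patients and associated percentage of patients in each category" (<25%, 25 to <50%, 50 to <75%, ≥75%), with no denominator stated.

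SAP 5.2 defines the descriptive statistics as "descriptive statistics such as the number of observations (n), mean, standard deviation, standard error, median, quartiles, minimum, and maximum". SAP Section 8 records no change of population or period for this endpoint.

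**The concern.** There are two separate issues.

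**Population.** A patient whose post-baseline values are all above 1.5×ULN has 0% of time at or below it, because interpolation between two values above the threshold never crosses it. That zero is an observed result, not missing data. Restricting the descriptive statistics to patients with at least one qualifying value removes patients because of their outcome, so the mean can only stay the same or rise.

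**Period.** The endpoint is listed for the extension, but the only planned calculation starts at the first post-baseline collections and so includes the loading phase. A child who met the threshold only before Month 6 enters the subset with positive time, although the value for the listed period is 0%.

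At stake is the planned summary of how long near-normalisation lasts in the extension. As written, its mean, SD, median and quartiles are planned neither in the stated population nor for the stated period.

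**Working it through.** The plan states no figure for this endpoint, so there is nothing to reproduce. N=20 is the planned enrolment (SAP 5.1), set by feasibility. The number of never-reachers m, the quartiles and the response courses below are illustrative assumptions.

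**1. Mean.** With m never-reachers at 0%, all-patient mean = reacher mean × (N−m)/N, so the reported mean is too high by the factor N/(N−m).

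| m | 20/(20−m) | All-patient mean if 70% is reported |
|---|---|---|
| 0 | 1.00 | 70% |
| 1 | 1.05 | 66.5% |
| 2 | 1.11 | 63% |
| 4 | 1.25 | 56% |

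**2. What can be recovered.** The mean follows from the reported n (SAP 5.2) and the set size (SAP 6.1). The SD follows too: with n reachers, mean x̄ and SD s, the sum of squares is (n−1)s² + n·x̄², and never-reachers add zero to it.

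The median and quartiles can in general only be bounded from the summary tables. Take m=4. The 10th and 11th of 20 ordered values are the 6th and 7th of the 16 reachers. The reacher Q1 is the mean of the 4th and 5th, and the reacher median is the mean of the 8th and 9th. Suppose these are 55% and 80%. The quartiles alone place the all-patient median between 55% and 80%, and the 75% cut in the category table narrows this:

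- 6th and 7th both below 75%: between 55% and 75%.
- One on each side: from (55+75)/2 = 65% to (75+80)/2 = 77.5%.
- Both at or above 75%: 75% to 80%.

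**3. Period.** Visits are monthly from Month 1 to 6 (Protocol Table 1), then every 3 months to Month 60 (Protocol Table 4, patients ≥10 kg). Assumed multiples of ULN are 4.0 at Month 1, 2.5 at Month 2, 1.4 at visits meeting the threshold and 2.0 at visits after leaving it.

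- Crossing in: 2 + (2.5−1.5)/(2.5−1.4) = Month 2.909.
- Crossing out: (1.5−1.4)/(2.0−1.4) = one sixth of the way through the interval. Leaving between Months 12 and 15 gives Month 12.5, between 6 and 9 gives 6.5, and between 5 and 6 gives 5.17.

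The whole-study window is Months 1 to 60 (59 months). The extension window is 54 months if the Month 6 predose value anchors it, or 51 months if it starts at the first later collection (Month 9).

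| At threshold | Whole study | Extension from Month 6 | Extension from Month 9 |
|---|---|---|---|
| Months 3 to 60 | 57.09/59 = 96.8% | 54/54 = 100% | 51/51 = 100% |
| Months 3 to 12 | 9.59/59 = 16.3% | 6.5/54 = 12.0% | 3.5/51 = 6.9% |
| Months 3 to 6 | 3.59/59 = 6.1% | 0.5/54 = 0.9% | 0/51 = 0% |
| Months 3 to 5 | 2.26/59 = 3.8% | 0/54 = 0% | 0/51 = 0% |

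The whole-study value is lower for the sustained responder and higher for patients who lose the effect. Gaps are wider with short follow-up. With time counted from Month 0 to Month 12, a patient at threshold from Month 3 onward has 9/12 = 75% against 6/6 = 100%, and one at threshold only from Month 2 to 6 has 4/12 = 33.3% against 0%.

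**The case against.** **Unrestricted summaries are planned.** A reader might infer that the endpoint is summarised only in reachers. The documents do not support that. The subset wording attaches to the descriptive statistics. The category table follows without it and reads by default as the full set, with never-reachers in <25%, and the by-visit proportions are also unrestricted. This stands. What remains is that the category denominator is unstated and that <25% merges zero with small positive values.

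**The information is not lost.** The restriction is disclosed, the mean and SD can be back-calculated, and by-patient listings that mark the study period (SAP 5.2) would let a reader rebuild the rest. This also stands, but rebuilding from listings does not replace a planned summary.

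**m may be zero.** One qualifying value over up to 60 months is enough, and Protocol 1.4 aims for normal or near-normal levels. This is fair. For context only, SAP 10.3 Table 2 shows mean spot reductions of 60.0% to 70.2% from Day 85 to Day 169 in the earlier study. At those reductions a patient starting above 1.5/0.400 = 3.75 to 1.5/0.298 = 5.03 times ULN stays above the threshold. That study enrolled patients aged 6 or over, and baseline multiples of ULN for this population are not given.

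**Period.** SAP 4.1 provides for whole-study summaries of secondary endpoints, so that version is legitimate. SAP 5.2 says tables for each study period use that period's data, but it does not name this endpoint or give the formula a Month 6 start, so it does not supply the missing version. A reader might also infer that the whole-study window flatters the drug. The table above shows the direction varies, and the sustained responder scores lower.

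**Conventions.** The extension decimals depend on whether the Month 6 predose value anchors the window. SAP 4.1 puts data up to the Month 6 dose in the primary period, which favours Month 9 on a strict reading, but SAP 7.3 does not say. The mismatch is present either way.

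**Conclusion.** Both points hold in limited form.

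- **Population:** the descriptive statistics are conditioned on the outcome, against the population stated in the same section. The reported mean is at or above the all-patient mean by N/(N−m): 1.00 to 1.25 at N=20 for m from 0 to 4. The true size is unknown because m is not given.
- **Period:** the version for the listed period is not planned, and Section 8 records no change. This is a mismatch with the listed endpoint, not a bias in the drug's favour.

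The endpoint is secondary and descriptive, no formal hypothesis is tested, and the primary endpoint is unaffected. Severity is minor to moderate.

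**What to change.** In SAP 7.3:

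1. Make the main summary all Efficacy Analysis Set patients with valid collections in the period, counting those who never meet the threshold as 0%. Keep the reacher-only summary as a labelled supplement.
2. Compute the endpoint for Month 6 to end of study, as listed. State whether the Month 6 predose value anchors the interpolation or the window starts at the first later collection. Keep the whole-study version as supportive.
3. State that the category table uses the same full-set denominator.

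The cost is a few lines of SAP wording and one additional run of the same calculation. No new data are needed, and both existing summaries are kept. The reported percentage may be slightly less favourable.

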7.4. Exploratory Efficacy Analysis

Efficacy exploratory endpoints will be analyzed using the Efficacy Analysis Set generally.

To evaluate the changes in nephrocalcinosis, a renal ultrasound will be performed at baseline and 6, 12, 24, 36, 48 and 60 months. The ultrasound will measure the grade of medullary nephrocalcinosis (range: 0 to 3) where a higher grade indicates greater severity.

Changes in the grade of medullary nephrocalcinosis will be categorized in 3 groups ('no change', 'worsening' or 'improving'). Shifts in the grade of nephrocalcinosis from baseline to each post-baseline visit will be summarized. The distribution of patients by extent of change in nephrocalcinosis grade (i.e., number of grades by which nephrocalcinosis improved or worsened) from baseline to each post-baseline visit will also be summarized. At each post-baseline visit, the number and associated

percentage of patients in the following 4 categories of the overall change (i.e., accounting for both kidneys), 'no change', 'improving', 'worsening', and 'indeterminate (one kidney improving and one worsening)' will be presented. Descriptive statistics will also be generated.

To evaluate the changes in renal stone events, these events will be captured at baseline (i.e. historical information) and throughout the study. A renal stone event is defined as an event which includes at least one of the following: visit to health care provider because of a renal stone, medication for renal colic, stone passage, and macroscopic hematuria due to a renal stone.

Total number of patients with a renal stone event, total number of renal stone events and rate of renal stone events during each study period will be calculated. The rate is calculated as total

number of renal stone events divided by total number of on-study days of patients during the respective period. And 95% confidence intervals will be presented.

Changes in other PD markers (such as spot urinary and plasma glycolate) will be explored. Descriptive statistics of actual, absolute change and percent change in levels of these markers will be generated at baseline and each post-baseline visit (as applicable).

Change in growth parameters (z-scores) from baseline over time and changes in developmental milestones over time will be summarized descriptively. The achievement of developmental milestones over time is assessed using Vineland Adaptive Behavior Scales. Composite scores for developmental milestones are collected and summarized using Vineland Adaptive Behavior Scales, second version (Vineland-II). Vineland-II consists of 5 domains each with subdomains. The adaptive levels associated with the domain and subdomain composite scores will be categorized and shift tables will be generated, details in Section 10.5. Vineland-II scores of each domain, subdomain, and the adaptive levels will also be presented in by-patient listing.

Changes in healthcare resource use will be listed and patient experience, and caregiver experience will be summarized descriptively, details in Section 10.6.

Analysis of ADA is included in Section 7.8.

7.5. Pharmacodynamic Analysis

Analyses of pharmacodynamic (PD) endpoints based on urinary excretion and blood samples (i.e., spot urinary UOx:Cr ratio, 24hr urinary oxalate corrected for BSA, plasma oxalate, etc.) are included in primary/secondary/exploratory endpoints and described in Section 7.1 to Section 7.4. All PD analysis will be based on Efficacy Analysis Set.

7.6. Pharmacokinetic Analysis

Pharmacokinetic analyses will be conducted using noncompartmental methods. PK parameters will be calculated using a validated version of Phoenix® WinNonlin. All PK analysis will be based on PK Analysis Set.

Population PK analysis is planned for all patients in the study and will be described in a separate population PK analysis plan.

7.7. Safety Analyses

Primary safety analysis is a descriptive summary of frequency of AEs using the Safety Analysis Set. The primary safety parameter is treatment emergent Adverse Events (AEs). A treatment emergent AE will be defined as an AE that occurs or worsens on or after the first dose date/time of lumasiran through 84 days after the last dose of lumasiran. In addition, any AE that worsened in intensity or was subsequently considered related to study drug will be considered treatment emergent. Other safety parameters will include vital signs, ECGs, clinical laboratory assessments and physical exams.

Safety analysis will be conducted both at Month 6 interim analysis and end of study. AE analysis may be generated for potential interim analyses if applicable.

7.7.1. Adverse Events

AEs will be classified using the Medical Dictionary for Regulatory Activities (MedDRA Version 21.1 or later) and displayed in tables using System Organ Class (SOC) and Preferred Terms (PT). All treatment emergent AEs hereafter will be referred to as AEs in this document.

An overview table of AEs will be generated. The overview table will include the number and percentage of patients in categories such as, but not limited to:

- At least 1 AE
 - At least 1 drug related AE
- At least 1 severe AE
 - At least 1 drug related severe AE
- At least 1 Serious Adverse Event (SAE)
 - At least 1 drug related SAE
- At least 1 AE leading to treatment discontinuation
 - At least 1 drug related AE leading to treatment discontinuation
- At least 1 AE leading to study withdrawal
 - At least 1 drug related AE leading to study withdrawal
- Death

Tabulations by System Organ Class (SOC) and Preferred Term (PT) displaying the number of patients (percentage) and total events will be produced for the following tables:

- All AEs
- Severe AEs
- AEs by Maximum Severity
- AEs related to treatment
- AEs related to treatment by Maximum Severity
- All SAEs
- SAEs related to treatment
- AEs leading to treatment discontinuation
- AEs leading to treatment interruption
- AEs leading to study withdrawal

Tabulations by PT in decreasing order of frequency within the Safety Analysis Set will be generated for the following tables:

- All AEs
- All SAEs

- AEs related to treatment
- SAEs related to treatment

There will also be an All AE table generated displaying rates of AEs adjusted for exposure-time during the respective period.

Patients who report multiple occurrences of the same AE (preferred term) will be classified according to the most severe occurrence or most related.

Separate listings will be provided for deaths, SAEs, and AEs leading to discontinuation of study drug, dose interruption, or withdrawal from study. By-patient AE listings will be provided.

Additional summaries of injection site reactions (ISRs) and AEs mapping to the Drug related hepatic disorders Standardized MedDRA Query (SMQ) will be generated as described below. In addition, other SMQs or AE groupings may be evaluated.

Injection Site Reactions (ISRs): AEs mapping to the High-Level Term (HLT) Injection Site Reactions using MedDRA dictionary will be included in the summary. Frequency (percentages) of ISRs by HLT and PT will be generated. A separate listing will be generated to display all patients who reported ISRs. In addition, a table of the number of patients with at least 1 ISR, total number of injections, total number of injections complicated by ISRs and corresponding % of injections complicated by ISR with the most common signs and symptoms reported due to ISRs will be generated.

Hepatic AEs, including Liver Function Test (LFT) abnormalities: Analysis of hepatic AEs will include AEs mapping to the SMQ Drug-related hepatic disorders – comprehensive search (includes all narrow and broad terms). Frequency (percentages) of hepatic AEs will be summarized by SOC and PT. A separate listing will be generated of all patients reporting these events.

7.7.2. Dosing and Extent of Exposure

Summaries of exposure will include the following characteristics such as, but not limited to: the total number of doses received per patient, mean number of doses per patient, cumulative number of doses received, duration of drug exposure (months), the total dose administered (mg) and total volume administered (mL).

Definition of drug exposure (days) will be defined as the minimum of [Exposure time= (date of last exposure – date of first dose +1)] where date of last exposure will represent either the date of the last dose administered dose +84, analysis cut-off date or end of study date. The exposure during the primary analysis period will be right censored; that is, the date of the last exposure will not be later than the first date of dosing in the Extension Period.

Dose interruptions and compliance are not taken into account.

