**Table 1: Schedule of Assessments –Primary Analysis Period (Screening through Month 6): All Patients**

*After Month 6, patients with weight <10 kg follow Table 2. Patients with weight ≥10 kg follow Table 4.*

Study Period Study Visit	Notes	Screening	6-Month Primary Analysis Period							
			Baseline	Wk 2	M1	M2	M3	M4	M5	M6
Study Day (±Visit Window)		-60 to -1	1 (±3)	15 (±14)	29 (±14)	57 (±14)	85 (±14)	113 (±14)	141 (±14)	169 (±14)
Blood and urine samples for exploratory analyses	Single-void urine and blood sample collected predose or prior to visit. Section 6.6	X	X		X		X			X
Review/record AEs	SAEs are collected in the Screening period. Starting on Day 1, all AEs (ie, including SAEs) are collected. Section 6.5.6.2									Continuous
Prior and concomitant medications	Section 5.3									Continuous

Abbreviations: ADA=antidrug antibody; AE=adverse event; AGXT=alanine-glyoxylate aminotransferase gene; DNA=deoxyribonucleic acid; ECG=electrocardiogram; LFTs=liver function tests; M=Month; PD=pharmacodynamic; PH1=primary hyperoxaluria type 1; PK=pharmacokinetic; SAE=serious adverse event; Wk=Week

Note:

- One month is defined as 28 days.
- Assessments are to be performed prior to dosing, where applicable. When scheduled at the same time points and where feasible, the assessments of vital signs and 12-lead ECGs should be performed before physical examinations and blood sample collections.
- Visits and study drug dosing may be conducted offsite where applicable country and local regulations and infrastructure allow (at the discretion of the Investigator, based on safety and tolerability), provided the patient has tolerated a dose of lumasiran administered in the clinic. If a visit is conducted offsite, a body system assessment may be performed in lieu of a physical examination.
- In situations where a study visit is unable to be completed (either at the site or offsite by a healthcare professional), the Investigator (or delegate) will verbally contact the patient within the study visit window to assess concomitant medications, renal stone events, adverse events, and healthcare utilization.

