4. PATIENT POPULATION

4.1. Patient Definitions

The populations (analysis sets) are defined as follows:

- Safety Analysis Set: All patients who received any amount of lumasiran during study.
- Efficacy Analysis Set: All patients who received any amount of lumasiran and have at least one valid spot urinary UOx:Cr ratio value at baseline and at least one valid spot urinary UOx:Cr ratio value from assessment(s) at Month 3 through Month 6.
- Primary Interim Efficacy Analysis Set: Among first 16 enrolled patients, all patients who received any amount of lumasiran and have at least one valid spot urinary UOx:Cr ratio value at baseline and at least one valid spot urinary UOx:Cr ratio value from assessment(s) at Month 3 through Month 6
- PK Analysis Set: All patients who received one full dose of lumasiran and have at least one postdose blood sample for PK parameters and have evaluable PK data.

The Safety Analysis Set will be used for safety analyses and sensitivity analysis of efficacy. The Efficacy Analysis Set will be used to evaluate efficacy endpoints. The PK Analysis Sets will be used to conduct PK analyses of plasma lumasiran concentrations.

The primary analysis period is defined as the time period from the date/time of the first lumasiran dose administration until either the date/time of lumasiran dose administration at Month 6 or the date of the Month 6 visit (Day 169) for patients who discontinued treatment prematurely. Primary analysis will be conducted using all data collected in the Primary Analysis Period. All data up to the dosing at the Month 6 visit will be included in the Primary Analysis Period.

The extension period starts after the date/time of lumasiran dose administration at Month 6 until the end of the study. Analysis of Extension Phase will focus on long-term efficacy of lumasiran.

Duration of Study is defined as the time period from on or after the first date/time of lumasiran dose until the end of the study. Analyses of Duration of Study will summarize secondary endpoints using data collected during the entire study period. These analyses focus on long-term efficacy and safety effects of lumasiran during both the primary analysis period and the extension period.

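### Primary-period exposure is capped at the first Extension Period dose, which on the SAP's own definitions can fall after the primary-period AE window has closed

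*SAP*

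**What the plan says.** Four statements in the SAP have to work together.

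- **Where the periods meet (4.1).** For patients still on treatment the primary analysis period runs to the Month 6 dose: "All data up to the dosing at the Month 6 visit will be included in the Primary Analysis Period". For the others it ends at "the date of the Month 6 visit (Day 169) for patients who discontinued treatment prematurely". The next period follows: "The extension period starts after the date/time of lumasiran dose administration at Month 6 until the end of the study".
- **What a period table contains (5.2).** "Summary tables and figures for each study period will include all data collected during the corresponding period as defined in Section 4.1". Primary-period AEs therefore stop at the Month 6 dose, or at Day 169.
- **How exposure is measured (7.7.2).** Exposure is the date of last exposure minus the date of first dose, plus 1. It is taken as a minimum, where "date of last exposure will represent either the date of the last dose administered dose +84, analysis cut-off date or end of study date". For the primary period there is one further limit: "the date of the last exposure will not be later than the first date of dosing in the Extension Period".
- **Where exposure is used (7.7.1).** "There will also be an All AE table generated displaying rates of AEs adjusted for exposure-time during the respective period".

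The protocol schedules match SAP 4.1. Table 1, the primary-period schedule, carries the Month 6 dose for both weight groups. The extension schedules begin dosing at Month 7 for patients under 10 kg (Table 2) and at Month 9 for patients of 10 kg or more (Table 4).

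**The concern.** An exposure-adjusted rate needs its numerator and denominator to cover the same time. Section 4.1 closes the AE window at the Month 6 dose. If the extension starts only after that dose, the first dose inside the extension is the next one, at Month 7 or Month 9, and 7.7.2 allows primary-period exposure to run that far. The denominator would then contain weeks in which no event can be counted, and the primary-period AE rate would be understated. In a single-arm study no comparator carries the same error, so it would not cancel, and its direction favours the drug.

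A second gap does not depend on where the Month 6 dose belongs. The censoring clause is triggered by an extension dose. A patient who stops treatment before Month 6 never has one, so only the last-dose-plus-84 limit, the analysis cut-off and the end of study remain. None of these is tied to the Day 169 period end.

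**Working it through.** **Inputs.** Protocol Table 1: "One month is defined as 28 days". Nominal days from Protocol Tables 1, 2 and 4: Month 3 = 85, Month 4 = 113, Month 5 = 141, Month 6 = 169, Month 7 = 197, Month 9 = 253. The 84-day limit and the exposure formula are from SAP 7.7.2.

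**Reproducing the plan's own figure.** Study day = 28 × month + 1. Month 6 gives 28 × 6 + 1 = 169, the day stated in SAP 4.1. Months 7 and 9 give 197 and 253, as scheduled. With the first dose on Day 1, exposure to Day D is D − 1 + 1 = D days.

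**Literal reading, patients on schedule.** The SAP gives no rate formula; I assume events divided by summed exposure. With the events fixed, the rate is multiplied by 169 / (exposure as written).

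| Weight group | First dose after Month 6 | Exposure as written | AE window | Excess | Effect on rate |
|---|---|---|---|---|---|
| <10 kg | Month 7 | 197 days | 169 days | 28 days | 169/197 = 0.858, 14.2% too low |
| ≥10 kg | Month 9 | 253 days | 169 days | 84 days | 169/253 = 0.668, 33.2% too low |

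The 84-day limit does not prevent this if the Month 6 dose counts as the last dose: 169 + 84 = 253. For 20 patients with an assumed mix of 1 under 10 kg and 19 at or above, the denominator is 197 + 19 × 253 = 5,004 days, against 20 × 169 = 3,380. The ratio 3,380/5,004 = 0.675 makes the pooled rate 32.5% too low. Actual dosing dates within the visit windows would shift all these figures.

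**Last dose taken from before Month 6.**

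- ≥10 kg: Month 3 dose, 85 + 84 = 169. No excess.
- <10 kg: Month 5 dose, 141 + 84 = 225, then capped at the Month 7 dose. Exposure is 197 days, still 28 too many.

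**Month 6 dose read as the first extension dose.** Exposure is capped at Day 169 for both groups. No excess for patients on schedule.

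**Patients who stop before Month 6 (either reading).** There is no extension dose, so the limit is last dose + 84, provided the cut-off is later:

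- last dose Month 3: 85 + 84 = 169, no excess;
- last dose Month 4 (monthly dosing only): 113 + 84 = 197, excess 28 days;
- last dose Month 5 (monthly dosing only): 141 + 84 = 225, excess 56 days.

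If one patient of 20 stopped after Month 5 and the other 19 had 169 days each, the denominator would be 19 × 169 + 225 = 3,436. Then 3,380/3,436 = 0.984, so the pooled rate would be 1.6% too low.

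**The case against.** The strongest reply is that the censoring clause was meant to work at Month 6. SAP 7.3 and the protocol's objectives label the extension as running from Month 6 to the end of the study, and 6 + 54 months gives the stated 60 months of treatment. SAP 7.7.2 counts in dates while 4.1 uses date and time, so on the Month 6 calendar date dosing occurs and the extension opens. This reading also gives the clause work to do: a monthly-dosed patient whose Month 5 dose plus 84 reaches Day 225 is cut back to 169. On the literal reading, with Month 6 as the last dose, the clause adds nothing for quarterly patients, because 169 + 84 is already 253. The wording is also only an upper bound, and 7.7.1 asks for exposure during the respective period.

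Much of this stands. The benign reading is plausible and removes the excess for patients on schedule. The argument from redundancy is weaker for patients already well into the extension at the data cut-off: if their last dose is taken as the latest one given, the 84-day limit lies far off and the clause has work to do under either reading.

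What does not stand is that the text settles the matter. SAP 4.1 says the extension starts after the Month 6 dose, and Protocol Table 1 places that dose in the primary schedule. The reply also does nothing for early stoppers on monthly dosing. It is right that the consequences are narrow: SAP 7.7 makes AE frequency the primary safety summary, and no hypothesis test is attached to the rates.

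**Conclusion.** The exposure cap and the period definition do not match, and the SAP should align them. On the literal reading the primary-period exposure-adjusted AE rate is too low by up to 14% for patients under 10 kg and up to 33% for patients of 10 kg or more. These figures assume nominal visit days, a data cut-off late enough to include the next dose, and the Month 6 dose (or a later one) counted as the last dose.

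A reader might infer that the reported rates will be 14% or 33% too low. The documents do not support that. The clause is a ceiling; a cut-off soon after a patient's Month 6 visit shortens the excess; taking the last dose from before Month 6 removes it for quarterly dosing; and treating the Month 6 dose as the first extension dose removes it for everyone on schedule.

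The part that holds on every reading is smaller. Monthly-dosed patients who stop after the Month 4 or Month 5 dose can carry exposure to Day 197 or 225 against a Day 169 period end. The documents do not say how many such patients there will be.

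Only the primary-period exposure summary and the exposure-adjusted All AE table are touched. AE counts, patient percentages and all efficacy analyses are unaffected.

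**What to change.** In SAP 7.7.2, keep the minimum of last dose + 84, analysis cut-off and end of study, and replace the censoring clause with:

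> and, for the primary analysis period, not later than the end of that period as defined in Section 4.1 (the date of the Month 6 dose, or the Month 6 visit/Day 169 if no Month 6 dose is given).

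Count extension exposure from that point only for patients dosed at or after Month 6. State in 4.1 which period the Month 6 dose belongs to. The case of no Month 6 dose needs its own wording because Protocol 5.2.2 allows a dose to be treated as missed, and 4.1 gives no period end for a patient who misses Month 6 and continues.

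The new limit should stay a ceiling. A rule that exposure simply ends at Month 6 would override the 84-day limit for early stoppers: a patient dosed only on Day 1 would get 169 days instead of 1 + 84 = 85, which inflates the denominator again.

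The cost is one or two SAP sentences and a small programming change. The downside for the sponsor is that reported primary-period AE rates may become less favourable.
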